8.2.3.3 Unscheduled Visit

An Unscheduled Visit can take place at any time during the BRV Extension Period. The following assessments will be performed:

- Vital signs (blood pressure, heart rate, respiratory rate [including apneas], oxygen saturation [pulse oximetry], and body temperature)
- Physical and neurological examination (Sarnat scale for subjects with HIE; physical examination will include a check for the presence of skin rash and skin hypersensitivity)
- Safety laboratory assessments (hematology, biochemistry, liver enzymes, and endocrinology)
- AEs as reported by the Investigator
- AEDs, concomitant medications, and medical procedures
- Review of BRV dosing diary
- Infusion site reaction monitoring

For subjects who remain in the BRV Extension Period for a prolonged duration (ie, until they reach a PNA of 90 days), these assessments will be conducted at intervals of 30 (± 3 days).

8.2.3.4 Telephone Contact

For subjects receiving oral BRV at home, a Telephone Contact can be performed at any time during the BRV Extension Period. The following information will be collected by the Investigator:

- AEs
- AEDs, concomitant medications, and medical procedures

8.2.4 Down-Titration Period

A Down-Titration Period of up to 1 week is recommended for subjects who complete the Evaluation Period, but do not enter the BRV Extension Period, discontinue BRV during the Evaluation Period, or start the BRV Extension Period but do not continue into the long-term study for any reason. The Down-Titration steps and duration may be adjusted at the Investigator's discretion.

The following assessments will be performed:

- Vital signs (blood pressure, heart rate, respiratory rate [including apneas], oxygen saturation [pulse oximetry], and body temperature)
- Physical and neurological examination (Sarnat scale for subjects with HIE; physical examination will include a check for the presence of skin rash and skin hypersensitivity; to be performed on the first day of the Down-Titration Period only)
- Primary cause of seizure (HIE, hemorrhage, or infarction; CNS malformations; CNS infections; undetermined causes; to be performed on the first day of the Down-Titration Period only)

- N-PASS
- BRV administration
- At least a 1-hour video-EEG on the final day of the Down-Titration Period (during the Down-Titration Period, additional VEEGs can be performed at the Investigator's discretion)
- AEs as reported by the Investigator
- AEDs, concomitant medications, and medical procedures
- Infusion site reaction monitoring

8.2.5 Safety Follow-Up Period

Subjects will proceed to the Safety Follow-Up Period once they complete the Down-Titration Period. This visit will occur 30 ± 3 days after the final administration of BRV. The following assessments will be performed:

- Vital signs (blood pressure, heart rate, respiratory rate [including apneas], oxygen saturation [pulse oximetry], and body temperature)
- Physical and neurological examination (Sarnat scale for subjects with HIE; physical examination will include a check for the presence of skin rash and skin hypersensitivity)
- Body weight and length and head circumference
- Confirmation of the primary cause of seizure (HIE, hemorrhage, or infarction; CNS malformations; CNS infections; undetermined causes)
- N-PASS
- Safety laboratory assessments (hematology, biochemistry, liver enzymes, and endocrinology)
- AEs as reported by the Investigator
- AEDs, concomitant medications, and medical procedures
- Medical History (for subjects not entering the long-term study)

For subjects unable to return to the hospital due to COVID-19, the Safety Follow-Up Visit can be performed remotely. In this case vital signs, the physical and neurological examination, biometric and psychometric parameters, and the laboratory assessment may not be performed.

9 ASSESSMENT OF PHARMACOKINETIC VARIABLES

9.1 Pharmacokinetic sampling and handling

For the determination of plasma concentrations of BRV and BRV metabolites, up to 6 blood microsamples (60 μ L/sample) will be collected per subject in the Exploratory (3 to 6 blood microsamples) and Confirmatory Cohorts (up to 6 blood microsamples) at 3 predetermined timepoints per day. An additional microsample (60 μ L) will be collected per subject for the determination of plasma concentrations of concomitant AEDs (PB and PHT).

Pharmacokinetic samples will be obtained either through a venous or arterial catheter or taken from routinely performed heel-pricks. Blood for PK samples should be drawn from a line different to that of the BRV infusion. Three BRV PK samples of blood will be collected at the

following predetermined timepoints at the first day of the Evaluation Period: 30 to 60 minutes, 2 to 4 hours, and 8 to 12 hours after the start of the most recent BRV infusion. For the Exploratory Cohort the same timepoints apply to the second day of the 48-hour Evaluation Period. For the Confirmatory Cohort(s), the second set of 3 BRV PK samples will be collected at the same timepoints on 1 of the other days of the 96-hour Evaluation Period. It will be acceptable if these samples are drawn on different days. The AED PK sample should be collected 3 hours after the start of the initial BRV administration. The timepoints for the collection of PK samples are described in [Table 5–4](#) for the Exploratory Cohort and in [Table 5–5](#) for the Confirmatory Cohorts.

Additional opportunistic blood samples for the PK analysis (Leroux et al, 2015) may be obtained at the Investigator's discretion at any time during the Evaluation Period. As opportunistic blood samples will be taken from routine laboratory blood samples, they are not considered an additional burden for the neonates. The plan for microsampling in N01349 is consistent with blood sampling schema in other neonatal studies (Allegaert and van den Anker, 2015; Jullien et al, 2015; O'Hara et al, 2015; Zhao and Jacqz-Aigrain, 2015; Zhao et al, 2014).

Exact dosing and sampling times will be recorded in the eCRF. Sampling times of pre-determined PK samples may be subject to change after analysis and review of data from the Exploratory Cohort to complete the PK profile.

The full set of a subject's PK plasma samples will be shipped for analyses after the subject has completed the Evaluation Period.

9.2 Pharmacokinetic sample shipment

Instructions on blood sample collection, processing, storage, and labeling/shipping will be provided in the laboratory manual for this study. On arrival, the samples will be stored at -20°C, until analysis.

Shipments due to arrive over the weekend or holidays must be avoided. For PK samples collected over a weekend in the site, these should be stored at -20°C and must be shipped under frozen conditions (packaged with dry ice) to the central laboratory on the following Monday. Prior to any shipment, an agreement must be made with the analytical laboratory for receipt of the samples.

- Absolute reduction in average seizure burden measured by continuous VEEG from Baseline to the end of the 96-hour Evaluation Period
- Percent reduction in average seizure burden measured by continuous VEEG from Baseline to the end of the 96-hour Evaluation Period
- Proportion of BRV responders at the end of the 96-hour Evaluation Period
- Proportion of subjects who are seizure-free (100% reduction in seizure burden from Baseline) at 24 hours following the start of initial BRV treatment, categorized by subjects with nonsevere or severe seizure burden at Baseline
- Time to reduction in seizure burden for BRV responders (defined as the first timepoint when BRV responder criteria were met)
- Seizure freedom at the end of the Down-Titration Period
- Rate of at least 50% reduction in ENS frequency per hour from Baseline to the end of the 96-hour Evaluation Period
- Proportion of subjects who are seizure-free by time interval at 3 hours, at 3-hour intervals thereafter through 24 hours, and every 12 hours to 24 hours following the start of the initial BRV treatment
- Absolute difference in clinical seizures at the end of the 24-hour Evaluation Period from Baseline for neonates with motor seizures at the time of inclusion
- Percent difference in clinical seizures at the end of the 24-hour Evaluation Period from Baseline for neonates with motor seizures at the time of inclusion

10.2 Assessment of other efficacy variables

Other efficacy variables will include:

- Absolute and percentage reduction from Baseline in seizure burden at evaluation periods of 0 hours to 3 hours, >3 hours to 6 hours, >6 hours to 12 hours, >12 hours to 24 hours, >24 hours to 36 hours, >36 hours to 48 hours, >48 hours to 72 hours, and >72 hours to 96 hours after the start of initial BRV treatment
- Categorized percentage reduction from Baseline to the end of the 96-hour Evaluation Period in seizure burden (<-25% [worsening], -25% to <25% [no change], 25% to <50%, 50% to <80%, and ≥80%)

- Proportion of BRV responders by time interval at evaluation periods of 0 to 3 hours, >3 to 6 hours, >6 to 12 hours, >12 to 24 hours, >24 to 36 hours, >36 to 48 hours, >48 to 72 hours, and >72 to 96 hours after the start of initial BRV treatment
- Proportion of subjects who switch over from BRV to another AED during the 96-hour Evaluation Period
- Proportion of responders to other treatment during the 96-hour Evaluation Period (including at the end of the 96-hour Evaluation Period, and by time intervals: 0 hours to 3 hours, >3 hours to 6 hours, >6 hours to 12 hours, >12 hours to 24 hours, >24 hours to 36 hours, >36 hours to 48 hours, >48 hours to 72 hours, and >72 hours to 96 hours after the start of initial BRV treatment)

(A responder to other treatment is defined as at least 80% reduction in nonsevere seizure burden from start of other treatment to end of other treatment or at least 50% reduction in severe seizure burden from the initiation of other treatment to end of other treatment during the 96-hour Evaluation Period).

To further evaluate BRV efficacy, a descriptive comparison will be conducted of the main efficacy variable data from N01349 with published responder rates for one or more AED treatments from literature (historical control group matched in age and condition) effective for the treatment of neonatal seizures in subjects of similar age (<29 days of PNA) and condition (neonatal seizures as noted in N01349 eligibility criteria). A recent study (Weeke et al, 2016) provides response rates for second line AED treatment of neonatal seizures in a similar population and with primary endpoints comparable to N01349. Results from this study, as well as results from other studies available in the literature at the time of N01349 completion and with populations and efficacy endpoints comparable to N01349, will be used for these comparisons.

10.3 Seizure burden

Seizure burden is defined as the total minutes of ENS per hour. Seizure burden information will be recorded for the Confirmatory Cohorts via a continuous VEEG. Seizure burden at Baseline will be evaluated over a period of at least 1 hour (subjects with intermittent seizures) or up to 30 minutes (subjects in status epilepticus).

Electroencephalographic neonatal seizures are defined as EEG seizures occurring for at least 10 seconds.

Seizure counts/seizure burden will be based on data collected using continuous VEEG. The VEEG recording will be evaluated by the local physician or central reader to evaluate eligibility of the subject. The VEEG recordings will subsequently be confirmed and quantified by the central reader at the end of the study.

11 ASSESSMENT OF SAFETY

11.1 Adverse events

11.1.1 Definitions

11.1.1.1 Adverse event

An AE is any untoward medical occurrence in a patient or clinical investigation subject administered a pharmaceutical product that does not necessarily have a causal relationship with

this treatment. An AE can therefore be any unfavorable and unintended sign (including an abnormal laboratory finding), symptom, or disease temporally associated with the use of a medicinal (investigational) product, whether or not related to the medicinal (investigational) product.

In order to ensure complete safety data collection, all AEs occurring during the study (ie, after the signing of the ICF), including any pretreatment and posttreatment periods required by the protocol, must be recorded even if no IMP was taken but specific study procedures were conducted. This includes all AEs not present prior to the signing of the ICF and all AEs that recurred or worsened after the signing of the ICF.

Signs or symptoms of the condition/disease for which the IMP is being studied should be recorded as AEs only if their nature changes considerably or their frequency or intensity increases in a clinically significant manner as compared to the clinical profile known to the Investigator from the subject's history or based on assessments performed prior to the first administration of BRV.

11.1.1.2 Serious adverse event

Once it is determined that a subject experienced an AE, the seriousness of the AE must be determined. An SAE must meet 1 or more of the following criteria:

- Death
- Life-threatening

(Life-threatening does not include a reaction that might have caused death had it occurred in a more severe form).

- Significant or persistent disability/incapacity
- Congenital anomaly/birth defect (including that occurring in a fetus)
- Important medical event that, based upon appropriate medical judgment, may jeopardize the patient or subject and may require medical or surgical intervention to prevent 1 of the other outcomes listed in the definition of serious

(Important medical events may include, but are not limited to, allergic bronchospasm requiring intensive treatment in an emergency room or at home, blood dyscrasias that do not result in inpatient hospitalization, or the development of drug dependency or drug abuse).

- Initial inpatient hospitalization or prolongation of hospitalization

(A patient admitted to a hospital, even if he/she is released on the same day, meets the criteria for the initial inpatient hospitalization. An emergency room visit that results in admission to the hospital would also qualify for the initial inpatient hospitalization criteria. However, emergency room visits that do not result in admission to the hospital would not qualify for this criteria and, instead, should be evaluated for 1 of the other criteria in the definition of serious [eg, life-threatening adverse experience, important medical event].

Hospitalizations for reasons not associated with the occurrence of an AE [eg, preplanned surgery or elective surgery for a pre-existing condition that has not worsened or manifested in an unusual or uncharacteristic manner] do not qualify for reporting. For example, if a subject has a condition recorded on his/her medical history and later has a preplanned surgery

for this condition, it is not appropriate to record the surgery or hospitalization as an SAE, since there is no AE upon which to assess the serious criteria. Please note that, if the pre-existing condition has worsened or manifested in an unusual or uncharacteristic manner, this would then qualify as an AE and, if necessary, the seriousness of the event would need to be determined).

11.1.1.2.1 Anticipated serious adverse events

The following list of anticipated SAEs has been identified, as these events are anticipated to occur in the population studied in this protocol at some frequency that is independent of drug exposure:

- Respiratory distress syndrome
- Convulsion

This original list will remain in effect for the duration of the protocol.

In addition, the following are anticipated SAEs in babies with HIE:

Acute

- Anuria/kidney failure
- Clotting aberrations up to disseminated intravascular coagulation
- Hypotonia
- Blood pressure instability
- Cardio-respiratory failure
- Multiorgan failure
- Severe encephalopathy with coma
- Status epilepticus
- Cerebral oedema
- Death

Chronic

- Cerebral palsy
- Visual Impairment
- Epilepsy
- Learning Difficulties
- Behavioural Difficulties

These lists do not change the Investigator's obligation to report all SAEs (including anticipated SAEs) as detailed in Section 11.1.2.3.

11.1.1.3 Adverse events of special interest

An AE of special interest is any AE that a regulatory authority has mandated be reported on an expedited basis, regardless of the seriousness, expectedness, or relatedness of the AE to the administration of a UCB product/compound.

The following will be considered AEs of special interest for the study population:

- Autoimmune nephritis
- Nephritis
- Nephritis allergic
- Tubulointerstitial nephritis
- Tubulointerstitial nephritis and uveitis syndrome
- Potential drug-induced liver injury as indicated by:
 - Direct (conjugated) bilirubin >2 mg/dL
 - Condition requiring phototherapy or exchange transfusion due to elevation total of bilirubin values
 - AST, ALT or ALP values ≥ 3 x ULN according to the subject's GA and the site's normal values for that GA, with the following exception:

For subjects with perinatal asphyxia, if initial and peak LFT elevation occurs within 5 days after birth, and if the time course of the elevation of LFT is compatible with hepatic injury due to perinatal asphyxia (ie, peak LFT elevation within few days after birth, and subsequent normalization until up to day 14 after birth) only AST, ALT or ALP elevation ≥ 5 x ULN must be reported as an AE of special interest.

11.1.2 Procedures for reporting and recording adverse events

The subject's parent(s) or legal representative(s) will be given the opportunity to report AEs spontaneously. A general prompt will also be given at each study visit to detect AEs. For example:

“Did you notice anything unusual about your child's health (since your last visit)?”

The requirements for recording AEs are detailed in Articles 16 and 17 of the Clinical Trials Directive (CTD) 2001/20/EC1 published in 2001, which establishes specific provisions regarding the conduct of clinical trials, in particular relating to the implementation of GCP. Articles 16 and 17 of the CTD outline the legal obligations for both the Investigator and Sponsor for the recording and reporting of all AEs and reactions.

[figure not shown]
In line with GCP, from the signing of the ICF, the Investigator will evaluate the subject for occurrence of any AEs based on continued observation and medical notes throughout the study. Serious AEs, AEs that are considered related to the medicinal (investigational) product, AEs leading to discontinuation, BRV infusion site reactions, or AEs considered by the Investigator to be critical to the safety evaluation of the protocol will also be recorded on the Adverse Event eCRF. Further guidance on the reporting requirements for AEs is provided in [Figure 11-1](#). The

predicted and expected AEs for BRV are also provided in Section 11.1.1.2.1, and reporting requirements for serious AEs are detailed in Section 11.1.2.3 .

This document cannot be used to support any marketing authorization application and any extensions or variations thereof.

PUBLIC COPY

Figure 11–1: Adverse event reporting flowchart

AE=adverse event; BRV=brivaracetam; eCRF=electronic case report form; SAE=serious adverse event
This AE reporting flowchart details the decision-making process for recording AEs in the eCRF. Serious AEs and nonserious AEs (that are potentially related to the study drug, result in discontinuation, are considered BRV infusion site reactions, or are considered by the Investigator to be critical to the safety evaluation) are to be recorded in the eCRF. All AEs will be recorded in the subject's medical notes.

Examples of AEs critical to the safety evaluation of the protocol include:

- AEs that might alter the current benefit-risk assessment of BRV use in neonatal seizures
- AEs that would be sufficient to consider changes in the study protocol
- AEs that would be sufficient to consider changes in the overall conduct of the study

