11.2.1 Evaluation of PDILI

The PDILI IMP discontinuation criteria (Food and Drug Administration [FDA], Guidance for Industry, Drug-induced liver injury, 2009) for this study are provided in Section 6.3.1, with the accompanying required follow-up investigation and monitoring detailed below. All PDILI events must be reported as an AE and reported to the study site and Sponsor within 24 hours of learning of their occurrence. Any PDILI event that leads to discontinuation must be reported as an AE of special interest (see Section 11.1.1.3) and must also be reported as an SAE see Section 11.1.1.2).

Evaluation of PDILI consists of the diagnostic testing and continued monitoring included in Table 11–3 specific tests dependent on laboratory results and corresponding symptoms) and consultation with a local hepatologist (if applicable; discussed in Section 11.2.1.1). Additional investigation and monitoring may be required and adapted based on the diagnosis after the cause of the liver injury/abnormality is confirmed (details in Section 11.2.1.4).

The results of all monitoring, including laboratory testing and other testing, should be made available to the study site and Sponsor.

All initial tests resulting in abnormal hepatic laboratory values need to be repeated, but appropriate medical action must not be delayed while waiting for the repeat result.

Table 11–3 summarizes the required investigations and follow-up for PDILI.

This document cannot be used to support any marketing authorization application and any extension or variation thereof.
PUBLIC COPY

Table 11–3: Required investigations and follow-up for PDILI

Patient population	Laboratory value		Immediate		Follow-Up	
	ALT/ AST/ALP	Direct (conjugated) bilirubin ^a	Consultation requirements	Actions	Testing	Evaluation
Subjects without perinatal asphyxia	≥3xULN according to the subject's GA and site's normal value	NA	Hepatology consultation (see Section 11.2.1); Medical Monitor must be notified within 24 hours (eg, laboratory alert) and subject discussed with Medical Monitor ASAP ^b	Immediate, permanent IMP discontinuation.	Essential: Must have repeat liver chemistry values and additional testing completed ASAP (see Section 11.2.1.1); recommended to occur at the site with HCP.	Monitoring of liver chemistry values at least twice per week until values normalize, stabilize, or return to within Baseline values.
Subjects with perinatal asphyxia ^c	≥5xULN according to the subject's GA and site's normal value	NA				

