10.2.1 General summaries of AEs

A table with overall summary of AEs will be provided separately for Evaluation Period, Extension Period, Down-Titration Period, Safety Follow-up Period and for the entire study, the table will include:

- the numbers and percentages of subjects with at least one TEAE
- the number and percentage of subjects with serious TEAEs
- the number and percentage of subjects with non-serious TEAEs
- the number and percentage of subjects with a TEAE that led to permanent discontinuation of study medication
- the number and percentage of subjects with a drug-related TEAE
- the number and percentage of subjects with a drug-related serious TEAE
- the number and percentage of subjects with a severe TEAE
- the number and percentage of subjects with AE leading to death
- the number and percentage of subjects with TEAEs leading to death
- the number and percentage of subjects who died prior to the first BRV dose

The following summary tables of AEs/TEAEs will be provided by primary SOC and PT. Summaries will be presented by Exploratory Cohort and individual Confirmatory Cohorts and for overall combined Confirmatory Cohorts for the SS.

- Incidence of pre-treatment AEs

Pre-treatment AEs are defined as AEs that had onset strictly prior to the date/time of the first dose of BRV

- Incidence of TEAEs (for Evaluation Period, Extension Period, Down-Titration Period, Safety Follow-up Period and for the entire study)
- Incidence of serious TEAEs
- Incidence of non-serious TEAEs

- Incidence of TEAEs by maximum intensity
Each subject will be counted at most once per primary SOC or PT according to the maximum intensity of all AEs within that SOC or PT. Severe intensity will be assumed for AEs for which intensity is not specified.
- Incidence of drug-related TEAEs
Drug-related AEs are AEs for which the relationship to study medication is specified by the Investigator as Related or AEs for which relationship is not specified.
- Incidence of drug-related serious TEAEs
Drug-related AEs are AEs for which the relationship to study medication is specified by the Investigator as Related or AEs for which relationship is not specified.
- Incidence of TEAEs by relationship
- Incidence of non-serious TEAEs by relationship
- Incidence of serious TEAEs by relationship
- Incidence of fatal TEAEs by relationship
- Incidence of TEAEs leading to permanent discontinuation of study medication
- Incidence of TEAEs leading to death

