- Incidence of non-serious TEAEs above reporting threshold of 5% of subjects in any cohort
- Incidence of non-serious TEAEs above reporting threshold of 5% of subjects by relationship
- Incidence of TEAEs of Interest
Defines as a selection of TEAEs identified by UCB to be of interest to BRV. These are identified using an UCB Excel file.

For the incidence of serious TEAE, TEAEs leading to permanent discontinuation of study medication and TEAEs of interest, the summary of subject numbers will be reported.

Listings AE Glossary and all adverse events will be provided for all subjects screened.

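### Non-serious AEs reach the eCRF selectively, largely on judged relatedness, but the SAP tabulates TEAE incidence and relationship as if collection were complete

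*Protocol*

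**What the plan says.** **Collection.** Protocol 11.1.2 gives the eCRF rule twice. The body text lists "Serious AEs, AEs that are considered related to the medicinal (investigational) product, AEs leading to discontinuation, BRV infusion site reactions", and adds events the investigator considers critical to the safety evaluation. The note to Figure 11-1 repeats it: "Serious AEs and nonserious AEs (that are potentially related to the study drug, result in discontinuation, are considered BRV infusion site reactions", and so on, ending "critical to the safety evaluation) are to be recorded in the eCRF. All AEs will be recorded in the" subject's medical notes. The examples of a critical event set a high bar, such as a change in benefit-risk or in the protocol.

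Protocol 11.1.1.1 is broader: "In order to ensure complete safety data collection, all AEs occurring during the study", "including any pretreatment and posttreatment periods required by the protocol, must be recorded even if no IMP was taken". It does not say whether the record is the eCRF or the notes.

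Some events have other routes. Protocol 11.2.1 states: "All PDILI events must be reported as an AE and reported to the study site and Sponsor within 24 hours". AEs of special interest (11.1.1.3, 11.1.2.4), suspected infectious transmission (11.1.4) and clinically significant new or worsened examination abnormalities (11.3.1) must also be reported.

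**Analysis.** SAP 10.2 defines a TEAE by onset at or after the first BRV dose, with no reference to the recording rule. SAP 10.2.1 plans incidence of all TEAEs, of non-serious TEAEs, by maximum intensity and by relationship, including "Incidence of non-serious TEAEs by relationship" and "Incidence of non-serious TEAEs above reporting threshold of 5% of subjects in any cohort". The last also has a by-relationship version. SAP 4.2.2 makes the eCRF the source of the AE listings. Neither Protocol 13.4 nor SAP 3.10 mentions selective collection.

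**The concern.** A table headed as incidence of non-serious TEAEs is normally read as the share of babies who had such an event. Here it is the share who had one that passed an entry rule, and one entry condition is the investigator's causality opinion in an open-label study. Splitting the same events by relationship then reports, in part, the criterion used to select them.

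AEs are the only secondary safety variable (Protocol 4.3.1), there is no control arm, and this is the first BRV study in neonates (Protocol 2.3). Two misreadings are possible: that non-serious events were rarer than they were, and that a larger share of them was attributed to BRV than investigators actually attributed.

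**Working it through.** The documents give no figure to reproduce. The check is a comparison of text, then the direction of the bias, then an illustration on assumed inputs.

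**Step 1: which tables are touched.**

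- Serious TEAEs: all enter the eCRF, so these tables stand.
- Related non-serious TEAEs: all qualify for entry, so their count is not cut by design.
- Unrelated non-serious TEAEs: cut, unless they lead to discontinuation, are BRV infusion site reactions, are judged critical, or come by one of the narrow routes.
- The cut carries into the overall TEAE, non-serious, maximum-intensity and relationship tables, and into the Down-Titration TEAE summaries used for withdrawal and rebound (SAP 10.4.11).
- The pre-treatment AE table is also affected. A non-serious event before the first dose can hardly be BRV-related or a BRV infusion site reaction, so pre-dose and post-dose incidence are not collected alike.

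**Step 2: direction.** Let f be the true share of non-serious TEAEs judged related, and c the share of unrelated ones that still reach the eCRF. Then:

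- recorded share = f + (1 − f)c
- apparent related share = f / [f + (1 − f)c]

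For f between 0 and 1, the recorded share is below 1 whenever c < 1, and the apparent related share is then above f. With c = 1 both distortions vanish. For subject counts, omitting events can only lower the number of babies with any non-serious TEAE and leaves the number with a related one unchanged. SAP 4.2.2 and 10.2.1 count missing causality as related, which pushes the split the same way.

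**Step 3: illustration.** The values of f and c are assumptions, not trial data.

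| f | c | recorded share | apparent related share |
|---|---|---|---|
| 10% | 10% | 19% | 52.6% |
| 20% | 10% | 28% | 71.4% |
| 40% | 10% | 46% | 87.0% |
| 10% | 25% | 32.5% | 30.8% |
| 20% | 25% | 40% | 50% |
| 40% | 25% | 55% | 72.7% |

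For f = 20% and c = 10%: 0.20 + 0.80 × 0.10 = 0.28, and 0.20 / 0.28 = 71.4%.

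**Step 4: the 5% threshold (minor).** One baby is 1/6 = 16.7% of the Exploratory Cohort and 1/12 = 8.3% of a Confirmatory Cohort. Both exceed 5%, so every reported term passes. In the 36 combined Confirmatory subjects, 1/36 = 2.8% and 2/36 = 5.6%, so a threshold there would act.

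**The case against.** The strongest defence is that selective recording is a deliberate limit on burden in very sick newborns, openly stated in the protocol, and that the safety picture does not rest on non-serious AE tables. All serious events are captured whatever their causality, and seriousness is broad here: prolonged hospitalization alone qualifies, and blood pressure instability, hypotonia and convulsion are among the anticipated SAEs. Laboratory values, vital signs, N-PASS, Sarnat, Thompson and mechanical ventilation are analysed independently of AE causality. All of this stands. It justifies the collection rule and limits the consequences, but it does not justify presenting the output as unqualified incidence.

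Four stronger readings might be inferred, and the documents do not support them.

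- That the not-related rows will be nearly empty, or that 60 to 90% of non-serious TEAEs will be missing. With f from 10 to 40%, those figures need c = 0, yet the rule itself has entry routes other than relatedness and the protocol adds more.
- That Protocol 11.1.1.1 and 11.1.2 contradict each other. The first requires recording without saying where; the second puts all AEs in the notes and some in the eCRF. They can be read together, though a cross-reference would help.
- That rates cannot be compared with other BRV studies. Those studies' collection rules are not given, and SAP 10.2 plans no such comparison.
- That the 5% rule hides events. A threshold that filters nothing hides nothing; it merely has no function.

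**Conclusion.** The point holds as a mismatch between collection and analysis. Followed as written, the plan gives non-serious TEAE incidence that is too low and a related share that is too high. The direction rests on two premises: related non-serious events are entered as the rule requires, and at least some unrelated ones are not. The size cannot be computed from the documents; the ranges in the working only show that it could be material. Serious TEAE tables are unaffected, and the count of related non-serious TEAEs is not reduced by design. The threshold is a small separate defect. The Figure 11-1 flowchart itself was not available for this check, only its note, and the eCRF completion guidelines were not available either. Either could add entry routes.

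**What to change.** In SAP 10.2, define the analysed events as TEAEs that meet the eCRF recording rule of Protocol 11.1.2, and name the additional routes. Retitle and footnote the overall, non-serious, maximum-intensity, pre-treatment and Down-Titration AE tables to match. Either drop the non-serious by-relationship tables, including the threshold version, or state that their related/not-related split is selected on causality and will not be interpreted. This costs SAP text, titles and footnotes, with no new data.

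For the threshold, either remove it or apply it to the combined Confirmatory Cohorts (at least 2 of 36, 5.6%), and keep the full AE listing so that single-baby events remain visible. Pooling all 42 subjects is not advised: it mixes cohorts with different doses and Evaluation Periods, and would remove terms seen in two babies (2/42 = 4.8%).

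Entering every AE in the eCRF would remove the bias at source, but it changes the protocol's recording rule. It would need an amendment (Protocol 14.5) and more site work, and, without back-filling from the notes, would leave cohorts collected under different rules. That is a burden trade-off for the sponsor; the relabelling is enough to make the tables say what they contain.
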